### 9.5 Study Procedures

Refer to the SOEs (Appendix A) for timing of assessments. Additional details are provided as necessary in the sections that follow.

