### **9.5.13 Disease Assessment**

Unless otherwise specified as detailed in the SOEs ([Appendix A](#)), response assessment for phase 1 dose escalation and phase 2a dose finding will be made locally. Disease assessment will be conducted per the SOEs ([Appendix A](#)) and evaluated according to IMWG criteria ([Appendix E](#)).

In extenuating circumstances, such as during the COVID-19 public health emergency, patients may use an alternative site for imaging with prior notification to the sponsor or designee.

Serum and urine response assessments will be performed as indicated in the SOE ([Appendix A](#)).

Imaging tests for qualifying patients are to be performed every 12 weeks beginning with Cycle 3 only for patients with extramedullary disease at screening or when there is a clinical suspicion of extramedullary progression. Investigators will assess disease response/status. Response and relapse categories are described in [Appendix E](#).

CR should be confirmed with follow-up assessments of bone marrow aspirate (BMA), SPEP, UPEP, immunofixation of blood and urine, and serum FLCs as outlined in [Appendix A](#). One bone marrow assessment (locally) is required to document a CR; no second bone marrow confirmation is needed. At the time of collecting BMA samples to confirm CR locally, a BMA sample will be also collected for central analysis of MRD as the first pull.

Please note that to determine a response of sCR, bone marrow immunohistochemistry or immunofluorescence for the  $\kappa:\lambda$  ratio, as well as serum FLC assay, should be performed for all patients suspected to be in CR to meet this response category's requirements.

The disease assessments outlined in the following sections will be performed as shown in the SOEs ([Appendix A](#)).

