#### 9.5.13.10 *Central Laboratory Evaluations*

##### BMA for MRD

For all patients, a BMA for MRD sample to determine rate and duration of MRD negativity should be collected at screening at the same time as the BMA and biopsy procedure is performed for local disease assessment purposes. Additionally, when a CR is suspected based on laboratory values, per routine clinical practice ([Appendix E](#)), a BMA should be drawn for local disease assessment and central analysis of MRD. Additionally for patients with a confirmed CR, BMAs for MRD should be collected at 6, 12, and 24 months following CR confirmation. If a patient has an MRD[-] result for any of the on-treatment assessments, this will trigger yearly evaluations of MRD, until the patient progresses. However, if a patient does not have an MRD[-] result for any of the planned on-treatment assessments, no additional BMA for MRD will be required. These evaluations will be performed at a central laboratory.

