##### BMA for Cytogenetics

During the screening period, an additional 3 mL pull of bone marrow (fresh BMA) will be collected, on completion of the BMA for MRD sample collection, to centrally analyze a broad spectrum of cytogenetic abnormalities and [REDACTED], perform immunoprofiling, [REDACTED], [REDACTED], and plasma biomarker evaluation. Where country guidelines and/or regulations prohibit genomic analysis, a fluorescent in-situ hybridization will be used to evaluate

cytogenetic abnormalities and remaining biomarker assessments limited to immunoprofiling and plasma analysis.

[REDACTED]

[REDACTED]

[REDACTED]

[REDACTED]

[REDACTED]

[REDACTED]

[REDACTED]

[REDACTED]

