##### **ORR, MRD[-] CR Rate and MRD[-] Rate**

ORR is defined in Section 13.1.3.1. The analysis will be based on the response-evaluable population.

MRD[-] CR rate is defined as the proportion of patients who have achieved confirmed CR assessed by the investigator and MRD[-] status using a threshold of  $10^{-5}$ . The analysis will be based on the response-evaluable population.

MRD[-] rate is defined as the proportion of patients who have achieved MRD[-] status using a threshold of  $10^{-5}$ . The analysis will be based on the response-evaluable population.

All these endpoints will be summarized by mean proportions and 2-sided 95% exact binomial CIs for each dose level.

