x Blood samples for immunogenicity (ADA/NAb) testing will be collected at predose on indicated visits during the treatment period and, if possible, at the EOT and PFS FU visits. In case of an infusion reaction, blood draws should be performed for central evaluation of immunogenicity (see Section 9.5.16). On days when dosing is not required, samples may be collected at any point during the clinic visit.

y Only repeat tests in parentheses for patients terminating treatment due to progressive disease if they were not performed before for progressive disease determination at the last visit, and for patients in CR if not performed before for CR confirmation.

z End-of-treatment laboratory assessments are to be performed before the patient starting a new treatment or a maximum of 30 days (+10 days) after the last dose.

aa Patients who discontinue study drug treatment for reasons other than progressive disease will continue PFS follow-up every 4 weeks from the EOT visit until the occurrence of progressive disease, death, the start of subsequent systemic antineoplastic therapy, study termination, whichever occurs first.

bb OS follow-up continues every 12 weeks until death, study termination, or patient withdrawal.

cc At predose (before the administration of the first agent when drug combinations are administered) and also at 4 hours ( $\pm$ 60 minutes) after the end of infusion of modakafusp alfa.

dd Immediately after the bone marrow aspirate/biopsy obtained for local disease assessment at screening and for confirmation of a suspected CR, an additional 1 mL of BMA will be collected for evaluation of MRD and sent to a central laboratory for analysis. If a BMA/biopsy drawn before consent, within 5 weeks of first dose, is used for local

disease assessment at screening, the first BMA pull at screening will be drawn for the MRD sample. Additionally, BMAs will be requested for MRD assessment at the time of suspected CR, and at 6, 12, and 24 months following CR confirmation. If a patient has an MRD[-] result for any of the on-treatment assessments, this will trigger yearly evaluations of MRD, until the patient progresses. However, if a patient does not have an MRD[-] result for any of the planned on-treatment assessments, no additional BMA for MRD will be required.

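### At suspected CR, Section 9.5.13 makes the central MRD marrow the first pull, while schedule footnotes dd and cc take it after the local aspirate, and nothing says which prevails

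*Protocol*

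**What the plan says.** **Suspected CR, protocol body.** Section 9.5.13 (Disease Assessment) says that when marrow is taken to confirm CR locally, "a BMA sample will be also collected for central analysis of MRD as the first pull".

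**Suspected CR and screening, schedule.** Appendix A footnote dd (Tables 1 and 2, phase 1) reads "Immediately after the bone marrow aspirate/biopsy obtained for local disease assessment at screening and for confirmation of a suspected CR, an additional 1 mL" and sends that volume to the central laboratory for MRD. Footnote cc (Tables 3 and 4, phase 2a) has the same wording. Each footnote has one exception: if the local screening marrow was drawn before consent, "the first BMA pull at screening will be drawn for the MRD sample".

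**Screening, protocol body.** Section 9.5.13.10 says only that the MRD sample "should be collected at screening at the same time as the BMA and biopsy procedure is performed for local disease assessment purposes". For cytogenetics it does give a sequence: "an additional 3 mL pull of bone marrow (fresh BMA) will be collected, on completion of the BMA for MRD sample collection".

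**Later samples.** MRD marrow is also due "at 6, 12, and 24 months following CR confirmation", and yearly after an MRD-negative result. No order is given for these.

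**Status of the schedule.** Section 9.5 says "Refer to the SOEs (Appendix A) for timing of assessments" and adds that the sections after it hold further detail where needed.

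**Endpoints.** Protocol Section 13.1.3.2.1 states "MRD[-] rate is defined as the proportion of patients who have achieved MRD[-] status using a threshold of" 10^-5. MRD-negative CR rate and duration of MRD negativity use the same threshold. All three are secondary endpoints in both phases.

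**The concern.** The suspected-CR marrow is the first planned on-treatment MRD sample, so an MRD-negative status can first be called from it. Two instructions for one needle procedure mean that some sites could send the first aspirate for MRD and others a later one. Their results would then not have been obtained under the same conditions.

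If a later pull contains proportionately more blood, the measured clonal fraction falls. The resulting misclassification would run one way, towards negativity. The documents contain no sample-adequacy rule or minimum cell input for an MRD-negative call that would catch it. The protocol does treat sequence as something to specify, since it fixes the cytogenetics pull after the MRD pull.

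**Working it through.** **Step 1: set the provisions side by side.**

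| MRD sample | Protocol body | Footnotes dd and cc |
|---|---|---|
| Suspected CR | 9.5.13: first pull. 9.5.13.10: drawn with the local sample, no order | Extra 1 mL after the local aspirate/biopsy |
| Screening | 9.5.13.10: same occasion as the local procedure, no order | Extra 1 mL after the local aspirate/biopsy; first pull only if the local marrow predates consent |
| 6, 12, 24 months after CR, and yearly | No order | No order |

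Only the first row holds a direct contradiction.

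**Step 2: look for a reading that removes it.**
- The footnotes' first-pull exception is confined to screening, so it does not reach the on-treatment sample.
- If the local sample were a core biopsy alone, the extra 1 mL could be the first aspirate. But Sections 9.5.13 and 9.5.13.9.1 use a local aspirate to assess CR, so this does not work in general.
- Section 9.5 points to Appendix A for timing and to the sections after it for detail. It sets no precedence between them.

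**Step 3: size, under an assumption.** The plan states no MRD rate or dilution figure to reproduce. As a check on the interval method, the Clopper-Pearson limits in protocol Section 13.2 for n = 20 do reproduce: 12/20 gives (0.361, 0.809), 14/20 gives (0.457, 0.881), 16/20 gives (0.563, 0.943).

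Let D be the dilution factor of a later pull (assumed). Measured level = true level / D, so a true level f reads as negative when f / D < 10^-5. The misread range is 1 × 10^-5 ≤ f < D × 10^-5.

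| Assumed D | Upper end of misread range |
|---|---|
| 1.5 | 1.5 × 10^-5 |
| 2 | 2 × 10^-5 |
| 3 | 3 × 10^-5 |
| 5 | 5 × 10^-5 |

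Cell input matters too. The chance of sampling no clonal cell is exp(−cells × f / D). At f = 10^-5:

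| Assumed cells | D = 1 | D = 2 | D = 5 |
|---|---|---|---|
| 3 × 10^5 | exp(−3) = 5% | exp(−1.5) = 22% | exp(−0.6) = 55% |
| 1 × 10^6 | exp(−10) ≈ 0% | exp(−5) = 0.7% | exp(−2) = 13.5% |

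**Step 4: effect of one misread patient.** In a phase 2a arm of 20, 1/20 = 5 points. For example, 5/20 = 25% (95% CI 0.087 to 0.491) becomes 6/20 = 30% (0.119 to 0.543). Phase 1 rates are reported by dose level; with 3 to 6 patients per level, one patient is 1/6 = 17 to 1/3 = 33 points.

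**The case against.** The strongest reply is that the documents show an ambiguity and no demonstrated bias. Most of that stands.

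- **Dilution.** Nothing in the protocol or SAP says that later pulls are diluted. A reader might infer that the MRD-negative rate will be overstated. The documents do not support that: both the mechanism and its size are assumptions, and the number of patients in the affected range is unknown.
- **Which text sites follow.** A reader might infer that sites follow the footnotes because they sit under the schedule. Section 9.5 does not say so. The laboratory manual, which Section 9.5.14.1 names for sample handling, was not available and may fix the order. It would not remove the contradiction within the protocol.
- **Screening.** A reader might infer that the protocol requires the MRD sample to be the first pull throughout. The body says this only for the CR-confirmation sample, so at screening the footnotes contradict nothing.
- **False relapse.** A reader might infer that a diluted negative at CR followed by a first-pull positive at 6 months would count as loss of MRD negativity. No local aspirate is scheduled with the later samples, but no pull order is stated for them either, so this remains conjecture.
- **Cost to the local sample.** On the same dilution assumption, taking MRD first leaves the later pull for the local aspirate, on which the CR criterion of under 5% plasma cells rests. The point is fair, but Section 9.5.13 already implies that order.
- **Importance.** The MRD endpoints are secondary and descriptive, and the SAP has no hypotheses or decision rules. On treatment, MRD is sampled only at suspected CR and afterwards, so few patients may be affected.

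**Conclusion.** The contradiction holds for the suspected-CR sample in both phases and is established from the text alone. Its consequence is conditional: sites could draw the sample in different orders, and if later pulls are diluted, disease just above 10^-5 could be called negative.

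Under that assumption the error in MRD-negative rate and MRD-negative CR rate runs upwards, by 5 points per patient in a 20-patient arm. Its total cannot be derived from the documents. Duration of MRD negativity is also exposed, but in which direction cannot be said without an order for the later samples. DLTs, TEAEs and ORR are unaffected.

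Appendix G records, with an amendment that was not implemented, a sponsor decision not to proceed to phase 2a. The current text still contains that part, and the phase 1 footnote carries the same conflict either way. This is an internal inconsistency worth correcting, and it does not threaten the primary conclusions.

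**What to change.** 1. For the suspected-CR sample, reword footnotes dd and cc to the order in Section 9.5.13. For example: *At suspected CR, the first pull of marrow (1 mL) is sent centrally for MRD; the aspirate for local disease assessment is taken from the next pull.*
2. Check that the laboratory manual states the same order.
3. For screening and for the 6-, 12- and 24-month samples (and the yearly ones), state one order so that samples are comparable over time and across sites. This is a new specification, since the body is silent there. The cytogenetics pull can stay after the MRD pull.
4. Optionally, record the pull number with each MRD sample, so that any drawn in the other order can be identified.

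Items 1 to 3 cost a wording change in two footnotes, a check of the manual, and a sentence for the remaining time points. No procedure or volume is added. The small downside is that the local CR-confirmation aspirate becomes the second pull.

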## **9.11 Posttreatment Follow-up Assessments (PFS and OS)**

Patients who stop treatment for any reason other than progressive disease will continue to have PFS visits. The PFS visits should occur every 4 weeks from the EOT until the occurrence of progression, death, the start of subsequent systemic antineoplastic therapy, study termination, whichever occurs first. OS follow-up continues every 12 weeks until death, study termination, or patient withdrawal. Imaging tests for patients with extramedullary disease should be performed every 12 weeks or if new symptoms suggest progressive disease.

See the SOE ([Appendix A](#)) for appropriate assessments during follow-up.

NOTE: Treatment-related SAEs must be reported to the Global Pharmacovigilance department or designee. This includes deaths that the investigator considers related to study drug that occur during the posttreatment follow-up. Refer to Section [10.0](#) for details regarding definitions, documentation, and reporting of SAEs.

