Only the assessments from the start of treatment up to the earlier of confirmed disease progression or the start of subsequent anti-cancer therapy will be considered. Only subsequent systemic anti-cancer drugs are considered as anti-cancer therapy (radiotherapy and surgeries are not considered as systemic anti-cancer therapy for the purpose of this analysis). However, assessment after the treatment discontinuation will be considered. Subjects with only assessments of “Not Evaluable” or missing response will be treated as non-responders, i.e., they will be included in the denominator when calculating the percentage.

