OS is defined as the time from the date of first dose administration of any study drug to the date of death from any cause. Patients without documentation of death at the time of analysis will be censored at the date last known to be alive.

OS (months) = (date of death or censor – date of first dose + 1)/30.4375.

The analysis of OS will be based on the safety population.

OS will be summarized using KM method. The K-M curves, the 25th, 50th (median) and 75th percentiles, alone with associated 2-sided 95% CIs based on Brookmeyer and Crowley method, and the K-M probability estimates with 95% CIs at 3, 6, 9 and 12 months (or later time points if applicable) will be presented. The number of patients with events and the number of patients censored will be summarized. The OS follow-up time will be summarized and reported using the inverse KM method.

MRD[-] CR Rate

MRD[-] CR rate is defined as the proportion of patients who have achieved confirmed CR assessed by the investigator and MRD[-] status using a threshold of 10^{-5} .

The analysis of MRD[-] CR rate will be based on the response-evaluable population.

MRD[-] CR rate will be summarized by frequencies, percentages, and 2-sided 95% exact binomial CIs.

MRD[-] Rate

MRD[-] rate is defined as the proportion of patients who have achieved MRD[-] status using a threshold of 10^{-5} .

The analysis of MRD[-] rate will be based on the response-evaluable population.

MRD[-] rate will be summarized by frequencies, percentages, and 2-sided 95% exact binomial CIs.

Duration of MRD negativity

Duration of MRD negativity is defined as the time from the date of first documentation of MRD negativity to the first documentation of MRD positivity or confirmed progressive disease, or death due to any cause, whichever occurs first. Patients without documentation of MRD positivity or confirmed progressive disease will be censored at the date last known to be MRD negative.

Duration of MRD negativity (months) = (earliest date of MRD positivity or progression or death or censor – date of MRD negativity + 1)/30.4375.

The analysis of duration of MRD negativity will include only patients who have achieved MRD negativity with a threshold of 10^{-5} based on the safety population.

If data permits, duration of MRD negativity will be summarized using KM method. Otherwise, a listing will be generated.

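### Duration of MRD negativity has no cut at subsequent anti-cancer therapy, and the Protocol's stops for MRD sampling and for PFS follow-up do not agree

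*Protocol*

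**What the plan says.** **Analysis of MRD.** SAP 6.6.2.1 ends duration of MRD negativity at MRD positivity, confirmed progression or death. For everyone else: "Patients without documentation of MRD positivity or confirmed progressive disease will be censored at the date last known to be MRD negative". There is no reference to Table 1 and no mention of subsequent therapy. SAP 6.6.2.2 carries the rule over to phase 2a. The Protocol's definition (13.1.3.2.1) also omits subsequent therapy, and it does not list death as an event. For the rate, the SAP states "MRD[-] rate is defined as the proportion of patients who have achieved MRD[-] status using a threshold of" 10^-5, with no limit on the date of the qualifying sample.

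**Analysis of response.** For best overall response, SAP 6.6.1.2 considers "Only the assessments from the start of treatment up to the earlier of confirmed disease progression or the start of subsequent anti-cancer therapy".

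**Sampling.** Footnote dd (Appendix A Tables 1 and 2), with matching text in footnote cc (Tables 3 and 4), states: "BMAs will be requested for MRD assessment at the time of suspected CR, and at 6, 12, and 24 months following CR confirmation". It then adds: "If a patient has an MRD[-] result for any of the on-treatment assessments, this will trigger yearly evaluations of MRD, until the patient progresses". Section 9.5.13.10 is to the same effect.

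**Follow-up.** Protocol 9.11 ends disease visits earlier: "The PFS visits should occur every 4 weeks from the EOT until the occurrence of progression, death, the start of subsequent systemic antineoplastic therapy". Footnotes aa and z give the same stop. Section 9.8, however, keeps patients who leave study drug without progression in the posttreatment assessments until progression.

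**The concern.** A patient can leave study treatment in MRD-negative CR and start another regimen before progressing. For that patient the SAP closes response and DOR at the switch but leaves the MRD duration open. Later MRD results or death under the new regimen can then be attributed to modakafusp alfa plus daratumumab. DOR and MRD duration for the same patient would answer different questions.

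The Protocol adds a practical problem. One site could follow the MRD footnote and keep sampling until progression, while another could follow the PFS footnote and stop at new therapy. The amount of post-switch MRD data would then depend on how a site reads the schedule. MRD duration is a secondary endpoint in both phases, and few patients are likely to contribute, so one or two could set the shape of a curve.

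**Working it through.** No design figure in either document concerns MRD, so there is no stated MRD value to reproduce. The check compares rules and then works through assumed patients.

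**1. Rules at subsequent anti-cancer therapy in the SAP**

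| Endpoint | Rule |
|---|---|
| Confirmed response (6.6.1.2) | Both assessments must precede it |
| Best overall response (6.6.1.2) | Later assessments not considered |
| PFS (6.6.2.1, Table 1) | Censored at last adequate assessment before it |
| DOR (6.6.2.1) | Same as PFS |
| DCB, duration of disease control (6.6.2.2) | Table 1 |
| TTP (6.6.2.2) | None stated |
| Duration of MRD negativity | None stated |
| MRD[-] rate | None stated |
| MRD[-] CR rate | CR part cut through confirmation; MRD part none stated |

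**2. Effect on duration**

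The SAP formula is months = (end − start + 1)/30.4375, in days. Timelines are assumed, with one month = 30.4375 days, first MRD-negative result at month 6 and CR confirmed at about the same time. The 6-, 12- and 24-month marrows then fall at months 12, 18 and 30.

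- *Patient A:* negative at months 6, 12 and 30, switch at month 13, no progression.
  - As written, censored at month 30: (24 × 30.4375 + 1)/30.4375 = 24.0 months.
  - With a cut at the switch, censored at month 12: (6 × 30.4375 + 1)/30.4375 = 6.0 months.
- *Patient A, but month 6 is the only negative result before the switch:* 24.0 months as written; with the cut, (0 + 1)/30.4375 = 0.03 months.
- *Patient B:* as A up to the switch, no later MRD sample, death at month 20.
  - As written, an **event** at (14 × 30.4375 + 1)/30.4375 = 14.0 months.
  - With the cut, **censored** at 6.0 months.

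Patient A gains event-free time from the missing rule; patient B gains an event. The effect has no fixed direction. Patient B's event depends on the SAP definition, because the Protocol does not count death.

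After a switch, progression is hard to establish. SAP 6.6.1.2 generally requires both confirming assessments to precede subsequent therapy, with limited exceptions, and PFS visits have ended. One of the three terminating events is therefore largely unavailable, while a negative marrow could still extend the duration.

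**3. Effect on the rates**

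Yearly tests are done only in patients who already have an on-treatment MRD-negative result. They are already counted, so yearly testing adds 0 patients to either rate. The only route is a first negative result at a 6-, 12- or 24-month post-CR marrow taken after a switch.

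One such patient moves an arm of 20 by 1/20 = 5 percentage points. With an assumed count of 4, that is 4/20 = 20% (exact 95% CI 0.057 to 0.437) becoming 5/20 = 25% (0.087 to 0.491). The same exact method reproduces the plan's interval for 12/20, (0.361, 0.809).

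**The case against.** The best defence is that post-switch samples will rarely exist. PFS visits stop at new systemic therapy, only 12-weekly survival follow-up remains, and no visit is clearly planned for a marrow. The MRD footnote also limits itself: "if a patient does not have an MRD[-] result for any of the planned on-treatment assessments, no additional BMA for MRD will be required". It can be read as describing on-treatment tests. The endpoints are secondary and descriptive, no arms are formally compared, and the SAP offers a listing if data are too sparse for Kaplan-Meier. Keeping MRD data to progression is also a legitimate choice if made deliberately.

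Much of this stands, and it rules out four stronger readings that a reader might infer:

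- *The MRD rates are inflated.* Yearly testing cannot add a patient to either rate, and the CR in MRD[-] CR must be confirmed before new therapy. Only the narrow route in step 3 remains.
- *Negativity under another regimen will be credited to study treatment.* It can be. The documents conflict on whether the sample is taken.
- *The bias favours the dose with more toxicity withdrawals.* Later MRD positivity or death counts as an event, so the direction is open. Protocol 8.6.1.5 also allows daratumumab to continue after some modakafusp alfa withdrawals, so a toxicity withdrawal need not mean another regimen.
- *MRD is the only endpoint without the cut.* SAP 6.6.2.2 states none for TTP either, and the Protocol's own DOR definition does not name subsequent therapy.

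The defence does not close the gap in duration. Section 9.8 and footnotes dd and cc point to progression as the stop, starting new therapy is not a listed reason for study withdrawal (9.9), and a death after the switch is captured by survival follow-up whether or not a marrow is drawn.

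**Conclusion.** The point holds for duration of MRD negativity. The SAP's censoring rule omits the cut that it applies to confirmed response, best overall response, PFS, DOR, DCB and duration of disease control, and neither document gives a reason. The Protocol's MRD sampling stop does not match its PFS follow-up stop.

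For one patient the difference can be large: 24.0 against 6.0 months in patient A, or an event at 14.0 months against censoring at 6.0 in patient B. Across the study it is probably modest. Those timelines and the 4/20 count are assumptions; the documents give no MRD rate and no rate of switching without progression, so the number of affected patients could be zero. For the two MRD rates, the missing date limit is worth closing but is only a narrow possibility.

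**What to change.** 1. In SAP 6.6.2.1 and 6.6.2.2, apply the subsequent-therapy row of Table 1 to duration of MRD negativity: a patient who starts subsequent systemic anti-cancer therapy before MRD positivity, confirmed progression or death is censored at the last MRD-negative result before that therapy.
2. In the same sections, count only MRD samples taken before that therapy for MRD[-] rate and MRD[-] CR rate.
3. Reconcile the MRD sampling stop in footnotes dd and cc and Section 9.5.13.10 with the PFS follow-up stop in footnotes aa and z.

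The cost is one or two SAP sentences and a phrase in the Protocol. If the reconciled sampling stops at new therapy, some marrow procedures are avoided. The downside is that MRD durations are censored earlier, substantially so for a patient who switches, and deaths after a switch no longer count as events. Censoring at the switch also assumes that switching is unrelated to later MRD status, an assumption of the kind already made for PFS and DOR.
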